12.9.2.2.3 Kaplan-Meier Curve

Time to death will also be analyzed using Kaplan-Meier curves. X-axis will be the time (days) and Y-axis will be the survival probability. Censored values will be represented with symbol 'I' and stratified by treatment groups. Number of subjects at risk over time will be annotated below the X-axis.

In DDP: Figures 14.2.3.3 and 14.2.3.4

12.9.2.2.4 Listing

Death Details will be listed by subject.

In DDP: Listing 16.2.7.4

12.9.2.3 Proportion of Subjects Alive on Days 7, 14, 28, 60 and 90

Number and percentage of subjects alive on Days 7, 14, 28, 60 and 90 without the following will be summarized. Percentages will be based on FAS. Subjects who discontinued from the study early or whose survival status is inconclusive on respective day will be considered as failure (Not Alive).

- Ongoing use of vasopressors
- Ongoing intubation/mechanical ventilation
- Ongoing residence in an ICU
- New ongoing need for dialysis/renal replacement therapy (RRT)

The analyses described in Section 12.9.1.1 will be repeated for each day as part of secondary analyses.

In DDP: Tables 14.2.4.1 and 14.2.4.2, Listing 16.2.6.2, 16.2.6.3, 16.2.6.4

12.9.2.3.1 Proportion of Subjects Alive controlling for stratification factor

Additionally, the proportion of subjects alive on Days 7, 14, 28, 60 and 90 will be compared across treatment arms controlling for stratification factor (WHO Severity score at baseline) using a Cochran-Mantel-Haenszel (CMH) method will be reported for each day as mentioned above. The common Risk Difference along with associated 95% CI will be reported. Unadjusted p-value for testing the null hypothesis that there is no strong correlation between treatment and subject status will also be reported.

In DDP: Tables 14.2.4.3 and 14.2.4.4

12.9.2.4 Proportion of Subjects Discharged

Number and percentage of subjects who were discharged on or before Days 14, 28, 60 and 90 will be summarized by treatment group. Proportions within each treatment group along with 95% CI will be

provided using Clopper-Pearson method for each visit. Risk Differences between treatment groups and p-value from testing the null hypothesis that there are no differences between treatment groups will be reported based on Fisher's Exact test. The summary will be based on FAS and repeated for Per-Protocol Analysis Set.

Reference SAS Program:

```
/* 95% CI for binomial (exact Clopper-Pearson) */

proc freq Data=XXX alpha=0.05;
  by treatment;
  tables flag/binomial(level='1' exact);
run;

/* 95% CI for risk difference and p-value from Fisher's test */

proc freq Data=XXX alpha=0.05;
  tables treatment*flag/riskdiff(cl=exact);
  exact riskdiff fisher;
run;
```

In DDP: Tables 14.2.5.1 and 14.2.5.2 and Listing 16.2.6.2

12.9.2.5 Hospitalization due to COVID 19

Number and percentage of subjects re-admitted to an acute-care hospital and subjects who are ongoing hospitalization at Day 14 will be summarized. Descriptive summaries for Duration of COVID-19 illness before hospitalization and cumulative number of hospitalization days will also be summarized.

Number and percentage of subjects who have been to the ICU and subjects who are still in ICU at End of Study will be summarized. Descriptive summary for cumulative number of ICU days will also be summarized.

Number and percentage of subjects who had Intubation / Mechanical Ventilations and subjects who are still in Intubation / Mechanical Ventilations at End of Study will be summarized. Descriptive summary for cumulative number of Intubation / Mechanical Ventilations days will also be summarized.

All summaries will be based on FAS and per-protocol analysis sets. Percentages will be based on the corresponding analysis sets.

In DDP: Table 14.2.6.1 and Table 14.2.6.2

Hospitalization, ICU and Intubation / Mechanical Ventilations will be listed by subject.

In DDP: Listings 16.2.6.2, 16.2.6.3, and 16.2.6.4

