### 5.2.2. Secondary Endpoints

- Safety and tolerability
  - Incidence, causality, and severity of AEs (graded according to the National Cancer Institute [NCI] Common Terminology Criteria for Adverse Events [CTCAE] version 5.0) in rhu-pGSN vs placebo groups
  - Frequencies of new or worsening clinically significant laboratory abnormalities in rhu-pGSN vs placebo groups
  - Mortality rate irrespective of cause at Days 28 and 90
- Efficacy
  - Daily change in 9-point WHO severity score through at least Day 14 (including after discharge, where feasible)
  - All-cause mortality at Days 28 and 90; time to death (Kaplan-Meier survival analysis)
  - Proportion of subjects alive on Days 7, 14, 28, 60, and 90 without:
    - Ongoing use of vasopressors
    - Ongoing intubation/mechanical ventilation
    - Ongoing residence in an ICU
    - New ongoing need for dialysis/renal replacement therapy (RRT)
  - Proportion of subjects discharged to home or immediate prior residence by Day 28
  - Days on the ventilator
  - Length of stay (LOS) in hospital and in ICU (days)
  - Re-admission to an acute-care hospital up to Day 90
- PK
  - PK for rhu-pGSN including maximum concentration ( $C_{max}$ ), time to maximum concentration ( $T_{max}$ ), terminal half-life ( $T_{1/2}$ ), area under the curve from time zero to 8 hours ( $AUC_{0-8}$ ), area under the curve from time 0 to infinity ( $AUC_{inf}$ ) for Dose #1 within 15 minutes predose, and at 1 ( $\pm 15$  min), 2 ( $\pm 15$  min), 6 ( $\pm 30$  min), and 12 ( $\pm 30$  min) hours after end of administration (but prior to Dose #2); for Dose #3 within 15 minutes predose, and at 1 ( $\pm 15$  min), 2 ( $\pm 15$  min), 6 ( $\pm 30$  min), 12 ( $\pm 30$  min) and 24 ( $\pm 30$  min) hours after the end of administration (participants refusing these blood samplings can enter and remain in the trial).
- Immunogenicity
  - Presence of anti-pGSN antibodies on Days 1 (predose), 28, and 90

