## 7. STUDY POPULATION

### 7.1. Number of Subjects

Part 1: A total of 60 evaluable participants randomized 1:1 to rhu-pGSN:placebo (30:30 subjects).

Part 2: A total of 20 evaluable participants randomized 1:1 to rhu-pGSN:placebo (10:10 subjects).

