## 11. STATISTICS

### 11.1. General Overview

All subjects given e 1 dose of study drug will be included in the Full Analysis Set (FAS) according to actual drug received; non-completers will be counted as failures in the primary efficacy analysis. Subjects receiving all 3 doses and evaluable for the primary Day 14 endpoint will constitute the per-protocol population for efficacy assessment. WHO severity score will be recorded daily while the subject is hospitalized, after discharge through Day 14, where feasible, and at each follow-up visit.

AE data will be summarized for the FAS by actual drug received using counts and proportions of subjects having an AE, each AE type, and an AE of each System Organ Class. SAEs and reasons for any early discontinuation will be summarized similarly. All deaths will be categorized by cause of death as per investigator assessment and relationship to study drug and/or COVID-19

Immunogenicity will be assessed on Days 1(predose), 28, and 90 days in all participants. Antibodies against pGSN will be assayed from frozen specimens to determine whether the investigational product induces an antibody response in recipients.

For Part 1, binary efficacy endpoints will be compared between treatments via stratified Cochran-Mantel-Haenszel (CMH) test and, to accommodate continuous covariates, via logistic regression. Continuous efficacy and biochemical endpoints will be compared between treatments via mixed model repeated measures analysis or analysis of covariance, depending on whether repeated measures are available or not. Time-to-event analysis via stratified log rank test and Cox proportional hazards model may also be carried out as supplemental analyses.

For Part 1, exploratory analyses looking at biomarkers and outcomes in each treatment arm will be conducted. Other exploratory analysis to compare the efficacy endpoint data from the rhu-pGSN group from this study to that of external control data may be carried out if appropriate. Sample size may be increased to improve the precision of the estimates of between-treatment comparisons if appropriate and if drug supplies are available.

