12.9.2.6 Comparison of Days in Hospital, ICU and Ventilation

Cumulative number of days for Hospitalization, ICU and Intubation / Mechanical Ventilation will be compared across treatment groups using non-parametric Wilcoxon Rank Sum test. The test will be two-sided with level of significance of 5%. Descriptive summaries of cumulative number of days,

difference in treatment groups, 95% CI and unadjusted p-value will be reported. P-value will be from testing the null hypothesis that mean of cumulative days across treatment groups are same.

Reference SAS Program:

```
proc npar1way data=<data>;
  class <treatment>;
  var <days>;
run;
```

In DDP: Table 14.2.6.3 and Table 14.2.6.4

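### SAP 12.9.2.4 compares discharge with an unstratified Fisher's exact test, where the protocol names stratified CMH for Part 1 binary efficacy endpoints; SAP section 13 does not list the change, and it costs power by an amount that depends on unstated discharge rates

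*SAP*

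**What the plan says.** **Protocol.** Section 5.2.2 lists a binary secondary efficacy endpoint: "Proportion of subjects discharged to home or immediate prior residence by Day 28". Section 11.1 sets the method: "For Part 1, binary efficacy endpoints will be compared between treatments via stratified Cochran-Mantel-Haenszel (CMH) test", with logistic regression where continuous covariates are needed. The synopsis repeats this.

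**SAP.** Section 12.9.2.4 summarises discharge by Days 14, 28, 60 and 90. It gives Clopper-Pearson intervals per arm and a risk difference, and for the null hypothesis a p-value that "there are no differences between treatment groups will be reported based on Fisher's Exact test". The code requests "exact riskdiff fisher" on a two-way table with no stratum variable.

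Other binary efficacy endpoints are treated differently. Sections 12.9.1.1 and 12.9.2.3 use CMH for the alive-without-support composites. Section 12.9.2.3.1 adds a version stratified by baseline WHO score for the secondary days, with a common risk difference and 95% CI.

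Section 13 lists two changes to the planned analyses: WHO score on scheduled visits only, and no external-control comparison. The discharge test is not among them. The summary table in SAP 16.1 has no row for discharge, so no reason appears there either.

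**The concern.** Discharge is the only binary efficacy comparison that the SAP moves to Fisher's test, and nothing says why. A reader who relies on the protocol expects a comparison adjusted for baseline severity and gets an unadjusted one.

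The switch is not neutral. With two arms of 30, Fisher's test is well below its nominal level, and it ignores baseline WHO score, which the SAP adjusts for in the MMRM, the Cox model and the stratified CMH. Randomisation is not stratified by severity (protocol synopsis), so a chance imbalance in WHO score would go uncorrected. At stake is the sensitivity of one secondary comparison, and whether the SAP follows the protocol or says openly that it does not.

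**Working it through.** **Inputs**
- Part 1: 60 evaluable, 30 per arm (protocol 7.1).
- Level: two-sided 5%, inferred. SAP 12.9.2.4 states no level for the p-value. It has "proc freq Data=XXX alpha=0.05" in the code and 95% CIs. The next test, the Wilcoxon in 12.9.2.6, says "The test will be two-sided with level of significance of 5" per cent.
- Discharge rates, effect size, severity mix and prognostic strength: not in the documents. All values below are assumptions.

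**The plan's own figure.** The only power figure is for the primary endpoint: N=54, about 80%, 20% vs 5%, one-sided 0.2. With pooled variance and no continuity correction,

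n = [0.8416·√(2·0.125·0.875) + 0.8416·√(0.20·0.80 + 0.05·0.95)]² / 0.15² = [0.8416·(0.4677 + 0.4555)]² / 0.0225 = 26.8, so 27 per arm and N=54.

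It reproduces. There is no corresponding figure for discharge.

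**Step 1: size and power at 30 per arm, by full enumeration.** For a and b discharged in the two arms, with m = a + b and N = 60:
- Unstratified CMH: Q = (a − m/2)² / V, with V = 30²·m·(N − m) / [N²(N − 1)], referred to chi-square on 1 df.
- Size at rate p: the sum over all 31×31 outcomes of Bin(a; 30, p)·Bin(b; 30, p), counting those with P ≤ 0.05. Power uses two different rates.

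| True rate, both arms | Fisher size | CMH size |
|---|---|---|
| 30% or 70% | 2.61% | 4.87% |
| 40% or 60% | 2.59% | 4.88% |
| 50% | 2.74% | 5.19% |
| 80% | 2.22% | 4.90% |
| 90% | 0.94% | 5.44% |

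| Discharge rates | Fisher power | CMH power | Loss (points) |
|---|---|---|---|
| 50% vs 90% | 91.4% | 94.9% | 3.5 |
| 50% vs 70% | 25.9% | 35.1% | 9.2 |
| 60% vs 85% | 48.9% | 59.5% | 10.6 |
| 70% vs 95% | 63.1% | 77.8% | 14.7 |
| 75% vs 95% | 43.6% | 63.3% | 19.7 |

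Where CMH power is 50–95% and neither rate exceeds 95%, the loss is about 4–20 points.

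**Step 2: one result by hand.** Take 20/30 vs 27/30 discharged. Then m = 47, V = 900·47·13 / (3600·59) = 2.589 and Q = 3.5² / 2.589 = 4.73, so CMH P = 0.030. Fisher gives P = 0.057.

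**Step 3: CMH stratified by WHO 4/5/6, by simulation.** Q = [Σ(a_k − E_k)]² / ΣV_k over the strata. Its size was 4.8–5.1%.
- *Score not prognostic* (60% in every stratum, mix 50/30/20%): odds ratio 3, 35.5% vs 44.7%; 4.5, 58.1% vs 66.9%; 8, 80.5% vs 87.0%. The loss is about 6.5–9 points.
- *Score prognostic* (mix 60/30/10%):

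| Placebo discharge in WHO 4/5/6 | Odds ratio | Fisher | Stratified CMH |
|---|---|---|---|
| 75/50/20% | 4 | 40% | 54% |
| 75/50/20% | 6 | 57% | 72% |
| 85/60/30% | 4 | 29% | 44% |
| 85/60/30% | 6 | 41% | 59% |
| 70/60/40% | 4 | 46% | 57% |
| 70/60/40% | 6 | 63% | 73% |

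The loss here is about 10–18 points. A stronger gradient (85/50/20%, mix 50/30/20%, odds ratio 4.5) gives 37.4% vs 56.7%, about 19. With overall placebo discharge near 80–85% the loss reaches about 24 (95/85/60%, odds ratio 8: 15.6% vs 39.9%). Unstratified CMH gains about as much in that last case (42.8%), so most of that loss comes from Fisher's conservatism rather than from ignoring the score.

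**Step 4: the replacement interval.** In the 60/30/10% prognostic scenarios, the Mantel-Haenszel 95% interval for the common risk difference excluded zero in about 6% of null trials. It disagreed with the CMH p-value in about 1% of null trials and 3–4% of trials with an effect.

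**The case against.** Fisher's test controls type I error and is conventional at this sample size. Because randomisation was not stratified, an unadjusted test is legitimate. SAP 8.1 describes the efficacy analyses as descriptive, and 8.2 asks for caution with secondary tests, so no decision rests on this p-value. All of that stands, and it limits the point to a modest one.

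Four stronger readings are tempting, and the documents do not support them:
- *That the SAP wastes half of a stated 5% error.* No level is stated for this p-value. The code option accompanies 95% intervals, and the explicit two-sided 5% belongs to the Wilcoxon test.
- *That the choice contradicts the sponsor's view that false negatives matter as much as false positives.* That statement justifies the one-sided 0.2 for the primary endpoint (protocol 11.2, SAP 12.9.1.1) and is not extended to secondary endpoints.
- *That the loss is 10–18 points as a fact.* This follows only from assumed rates, an assumed severity mix, large odds ratios and a prognostic score. The documents give no data on how WHO score relates to discharge.
- *That stratified CMH with a Mantel-Haenszel interval makes p-value and interval agree.* The two use different variances, and step 4 shows that they sometimes part.

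None of this explains why discharge departs from the protocol's method, or why section 13 is silent on it.

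**Conclusion.** The firm finding is an undeclared inconsistency between protocol and SAP for one secondary endpoint. It needs no assumptions. The direction of its effect is also clear at 30 per arm and an inferred two-sided 5% level: Fisher's real size is about half of nominal for mid-range discharge rates and about a fifth at 90%, while CMH stays close to 5%.

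The power cost can only be given as the range in steps 1 and 3, from about 4 to about 24 points. The high end needs either high discharge rates or a clearly prognostic WHO score. A reader might infer that the discharge analysis is invalid or that the trial's main conclusion is weakened. Neither follows: the test errs on the safe side for false positives, and the primary analysis does not use it. The change is worth making because it returns to the protocol's own method at almost no cost.

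**What to change.** In SAP 12.9.2.4, replace the sentence on the between-group test with wording such as: *Discharge by each day will be compared between treatment groups by the CMH test stratified by baseline WHO severity score. The Mantel-Haenszel common risk difference and its 95% CI will be reported. Fisher's exact test will be given as a sensitivity analysis.* State the two-sided level in words. Keep the Clopper-Pearson intervals per arm. In the code, add a line such as `tables bsl_who*treatment*flag / cmh riskdiff(common) alpha=0.05;`.

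If the sponsor prefers Fisher as the main comparison, list the departure in section 13 with its reason.

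Cost: a few sentences and lines of code, with no new data. Downsides to record:
- The method is asymptotic, and a stratum may be sparse. A stratum holding 10% of subjects would average 3 per arm.
- The Mantel-Haenszel interval is slightly anti-conservative in simulation.
- The interval can occasionally disagree with the CMH p-value, so the SAP should not promise agreement.

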4.2 Sample Size Justification

The primary endpoint is difference between treatments in the proportion of surviving subjects off vasopressors, the ventilator, and dialysis on Day 14. Here the power for the study is computed for the expected increase in proportion of surviving subjects without these supports at Day 14 after start of study treatment. A total sample size of N=54 has ~80% power to yield a statistically significant (alpha=0.2 1-sided) difference if the TRUE underlying proportions are 20% and 5% for placebo plus SOC and rhu-pGSN plus SOC, respectively. The minimum OBSERVED difference from placebo plus SOC proportion 20% that yields statistical significance is 8.4% (20% vs 11.6%). As this is a pilot Phase 2 POC trial in an infection with no approved therapy and false negative error (100% minus power) is equally as important as false positive error, the one-sided type 1 error is set at 0.2. Thus, the trial is adequately powered for its primary POC objective.

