4.5 Inclusion/Exclusion Criteria

4.5.1 Inclusion Criteria

To be considered eligible to participate in this study, a subject must meet all the inclusion criteria listed below:

- 1) Hospitalized with laboratory-confirmed (RT-PCR+) or highly suspected (compatible with at least bilobar lung involvement without another plausible diagnosis) COVID-19
- 2) Age ≥ 18 years
- 3) Weight ≤ 100 kg
- 4) Within 24 hours of reaching a WHO severity score of 4-6 either:
 - a) At admission
 - b) While already hospitalized.
- 5) Informed consent obtained from subject/next of kin/legal proxy
- 6) Primary admitting diagnosis of pneumonia supported by a compatible clinical presentation with a documented infiltrate consistent with pneumonia on CXR or CT, as assessed by the admitting emergency department (ED), clinic, or ward physician or equivalent caregiver
 - a) Recommended (not mandatory) guidance/discretionary criteria defining patients with pneumonia satisfying all 4 categories below:
 - i) At least 2 symptoms: difficulty breathing, cough, production of purulent sputum, or chest pain
 - ii) At least 2 vital sign abnormalities: fever, tachycardia, or tachypnea (thresholds -- fever: oral or core temperature $>100.4^{\circ}\text{F}$ [38°C]; heart rate >100 beats/min; respiratory rate >24 /min)
 - iii) At least one finding of other clinical signs and laboratory abnormalities: hypoxemia (O_2 saturation $<90\%$), clinical evidence of pulmonary consolidation, or leukocytosis $\geq 1.5 \times 10^4$ or leukopenia $<4 \times 10^3$
 - iv) Chest imaging or CT chest showing at least bilobar pulmonary infiltrates

- (1) Principal Investigator (PI) to note radiologic findings in the eCRF
- (2) Radiology report to be placed in the eCRF
- (3) A copy of the radiograph attached to be saved for review

b) A hyperinflammatory status (defined by increased ferritin $\geq 500 \mu\text{g/L}$, D-dimer $\geq 1000 \text{ ng/mL}$, or CRP $\geq 75 \text{ mg/L}$)

7) During the course of the study starting at screening and for at least 6 months after their final study treatment:

- a) Female subjects of childbearing potential must agree to use 2 medically accepted birth control methods
- b) Male subjects with a partner who might become pregnant must agree to use reliable forms of contraception (i.e., vasectomy, abstinence), or an acceptable method of birth control must be used by the partner
- c) All subjects must agree not to donate sperm or eggs (ovocytes)

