10.4 Full Analysis Set

All subjects given ≥ 1 dose of study drug will be included in the Full Analysis Set (FAS) according to actual drug received.

The FAS is the primary analysis set to analyze all efficacy endpoints. Subject disposition, demographic and baseline characteristics of the FAS will also be presented. Subjects will be analyzed according to the treatment group they actually received. Differences between planned and actual treatment, if any, will be discussed during the blinded review meeting.

Note: if a subject had inadvertently taken the study drug without randomization and/or had negative COVID RT-PCR results post study drug administration, the subject would still be included in the Full analysis set.

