10.6 Per-Protocol Analysis Set

The Per-Protocol Analysis Set includes all subjects who completed Day 14, took all three doses, and had no important protocol deviations that may affect the primary endpoint of the study.

The exclusion of subjects from the per-protocol analysis set will be discussed and finalized during the blinded review meeting prior to DBL. Protocol deviations that can potentially unblind treatment codes will be reviewed independently by authorized personnel and its impact on population flags will be confirmed prior to DBL.

The PPAS is also used to analyze efficacy endpoints. Demographic and baseline characteristics of the PPAS will also be presented. Subjects will be analyzed according to the treatment group they actually received.

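### Re-admission to Day 90 is shown only as a percentage of the whole analysis set, so subjects who die in or never leave the index hospital stay count as not re-admitted

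*SAP*

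**What the plan says.** Protocol 5.2.2 and SAP 7.2.2 list "Re-admission to an acute-care hospital up to Day 90" among the secondary efficacy endpoints. Its only planned analysis is in SAP 12.9.2.5: "Number and percentage of subjects re-admitted to an acute-care hospital and subjects who are ongoing hospitalization at Day 14 will be summarized". That section runs its summaries on the FAS and on the per-protocol set, and fixes the denominator: "Percentages will be based on the corresponding analysis sets".

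Neither set is limited to subjects who have gone home. SAP 10.4 says "All subjects given ≥ 1 dose of study drug will be included in the Full Analysis Set (FAS) according to actual drug received". SAP 10.6 says "The Per-Protocol Analysis Set includes all subjects who completed Day 14, took all three doses", and also excludes important deviations that bear on the primary endpoint. All subjects are inpatients at entry: the first inclusion criterion in SAP 4.5.1 begins "Hospitalized with laboratory-confirmed (RT-PCR+) or highly suspected".

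For re-admission the SAP plans a count and a percentage. It gives no test, no confidence interval and no rule for subjects who die. The rule that counts early discontinuation or unknown survival status as failure appears in SAP 12.9.1.1 and 12.9.2.3 and covers only the alive-without-support endpoints. The endpoint-to-method table in SAP 16.1 has no row for re-admission.

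**The concern.** A subject can be re-admitted only after leaving hospital alive. With the whole FAS as denominator, a death in the index stay is recorded in the same way as a subject who went home and stayed there, and that is the favourable result for this endpoint. A stay that never ends is treated likewise.

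The trial's primary question is survival without organ failure, so the arms may differ in how many subjects ever become able to be re-admitted. If the drug helps, more of its subjects reach that point, and the row would tend to count against it. If it harms, the row would tend to flatter it. With about 30 subjects per arm, one or two subjects can settle which arm looks better on an uncommon event.

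**Working it through.** **1. The plan's own figures.** The documents state no re-admission risk and no share discharged alive. The nearest design figures belong to the Day 14 primary endpoint. SAP 4.2 says "A total sample size of N=54 has ~80% power to yield a statistically significant (alpha=0.2 1-sided) difference" for proportions of 20% (placebo) and 5% (rhu-pGSN). These reproduce: a pooled-variance two-proportion z-test with one-sided alpha 0.2 and no continuity correction needs 27 per arm, has 80.1% power, and has a smallest significant difference of 8.4 points (20% vs 11.6%). The 20% and 5% are used below only as convenient values for a different quantity.

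**2. Formula.** Let *d* be the share of an arm never discharged alive, and *r* the re-admission risk among those discharged alive.

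- Percentage of the FAS = *r* × (1 − *d*)
- Percentage of those discharged alive = *r*
- With the same *r* in both arms, the ratio of FAS percentages (rhu-pGSN to placebo) = (1 − *d* on rhu-pGSN) / (1 − *d* on placebo), whatever the value of *r*

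**3. Illustration.** Assume *r* = 15% in both arms, and *d* = 20% on placebo and 5% on rhu-pGSN.

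- Placebo: 0.15 × 0.80 = 12.0%
- rhu-pGSN: 0.15 × 0.95 = 14.25%
- Gap: 2.25 points. At 30 per arm (Protocol 7.1) this is 30 × 0.0225 = 0.68 of a subject.
- Ratio: 0.95 / 0.80 = 1.19, with no difference in risk after discharge

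**4. Range.** All values of *r* and *d* are assumptions.

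| *r*, both arms | *d*, rhu-pGSN / placebo | FAS %, rhu-pGSN / placebo | Gap (points) | Gap (subjects of 30) | Ratio |
|---|---|---|---|---|---|
| 15% | 3% / 10% | 14.55 / 13.5 | 1.05 | 0.3 | 1.08 |
| 15% | 15% / 30% | 12.75 / 10.5 | 2.25 | 0.7 | 1.21 |
| 10% | 5% / 20% | 9.5 / 8.0 | 1.5 | 0.45 | 1.19 |
| 20% | 5% / 20% | 19.0 / 16.0 | 3.0 | 0.9 | 1.19 |
| 30% | 5% / 20% | 28.5 / 24.0 | 4.5 | 1.35 | 1.19 |
| 10% | 10% / 30% | 9.0 / 7.0 | 2.0 | 0.6 | 1.29 |
| 20% | 10% / 30% | 18.0 / 14.0 | 4.0 | 1.2 | 1.29 |
| 30% | 10% / 30% | 27.0 / 21.0 | 6.0 | 1.8 | 1.29 |

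**5. When the direction fails.** Take *r* = 20% and *d* = 5% in one arm, giving 19.0% of the FAS. An arm with *d* = 20% shows the same 19.0% if its own *r* is 0.19 / 0.80 = 23.75%, and shows more re-admissions if its *r* is higher than that.

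**6. Against sampling error.** For 12.0% vs 14.25% at 30 per arm, the standard error of the difference is √(0.12 × 0.88/30 + 0.1425 × 0.8575/30) = 8.7 points, against a distortion of 2.25 points.

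**7. Can the at-risk number be rebuilt from other tables?** Not from the summary tables.

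- The discharge table (SAP 12.9.2.4) depends on SAP 11.16.5, which classifies a subject with several stays by the latest one. A re-admitted subject's first discharge is therefore obscured. That rule also does not say that the discharge must be alive.
- SAP 12.10.2 tabulates deaths by arm, but not by whether they came before or after the index discharge.
- Only the subject listings would give the number.

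**The case against.** The strongest reply is that re-admissions over the FAS are a legitimate quantity: the crude incidence of re-admission by Day 90 among treated subjects, with death as a competing event. It keeps every dosed subject in the comparison. The alternative denominator, subjects discharged alive, selects on something that happens after randomisation, so it is no cleaner a treatment effect. This stands. A reader might infer that the FAS percentage is wrong and should be replaced. The documents do not support that; what is missing is the information that should stand beside it.

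A reader might also infer that the arm with more in-hospital deaths must show fewer re-admissions. That needs similar risk after discharge in the two arms, which the documents neither state nor imply, and step 5 shows how it can fail.

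Nor is the ratio of 1.19 derived from the plan's own figures. The 20% and 5% describe a Day 14 composite. Read as failure proportions, they include subjects alive on support at Day 14 who may go home later, so they need not match the share never discharged alive.

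The row is also descriptive and untested, and the distortion is small beside sampling error. Deaths, Kaplan-Meier survival at Days 28 and 90, discharge proportions and total hospital days are all reported by arm. That limits the harm. It does not remove it, because none of those tables gives the number at risk of re-admission or combines death with re-admission.

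**Conclusion.** The point holds as a gap in how a listed secondary efficacy endpoint is presented. As SAP 12.9.2.5 is written, subjects who die in or never leave the index stay are counted as not re-admitted, and no other planned summary corrects for this.

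The direction (fewer re-admissions shown in the arm with more in-hospital deaths) rests on similar risk after discharge in both arms. The size rests on assumed values throughout: about 0.7 of a subject per 30 in the illustration, and up to about 2 under the wider ranges. The effect may be smaller in the per-protocol set, because the requirement to complete Day 14 may remove early deaths; later in-hospital deaths and subjects never discharged would remain.

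The primary analysis and the sample size are not affected. The change is worth making because it is cheap and because the row, read alone, gives credit for death.

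**What to change.** In the SAP 12.9.2.5 table, keep the FAS count and percentage of subjects re-admitted, and add by arm:

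- (a) the number discharged alive from the index (first) hospitalization, the number who died before that discharge, and the number still in the index stay at Day 90;
- (b) re-admissions as a percentage of those discharged alive, labelled descriptive;
- (c) died or re-admitted by Day 90, over the FAS, as the between-arm summary.

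Item (c) keeps every dosed subject and cannot reward death. Items (a) and (b) let a reader see how many subjects could have been re-admitted. The index stay should be named explicitly, because the latest-hospitalization rule in SAP 11.16.5 would otherwise apply.

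The cost is a few extra rows, built from the hospitalization dates used in SAP 11.16.1 and the death dates used in SAP 11.18, with no new data collection. The one statistical downside is that (b) is conditional on a post-randomisation event, so it should not be read as a treatment effect.
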